## **5.6.4 Suitability of Subject Population**

This study plans to enroll both HCV treatment-naïve and IFN (IFN and pegIFN with or without RBV) treatment-experienced subjects from  $\geq 3$  to 17 years old with genotype 1 or 4 HCV infection as agreed upon in the PIP and PSP. The older subjects who are willing to swallow the adult formulations and are  $\geq 45$  kg will be studied with the adult coformulated tablets. For the younger children in the  $\geq 3$  to 8 and  $\geq 9$  to 11 year old age groups, a mini-tablet formulation of all the DAAs and RTV will be used for ease of

administration. In addition, RBV oral solution will be available in the study for children who cannot take the RBV tablets.

### **5.6.5 Selection of Doses in the Study**

In the Pediatric Investigation Plans (PIP) and the Pediatric Study Plan (PSP) for ombitasvir/paritaprevir/ritonavir and dasabuvir, the proposed pediatric doses were based on providing comparable exposures to adult subjects.

AbbVie has recently developed separate mini-tablet formulations for ombitasvir, paritaprevir, ritonavir and dasabuvir for use in Part 1 of the present study.

The mg/kg doses as proposed in the PIP and PSP were used to calculate mg doses for a given weight range for each of the age groups. While this approach involved some approximation of doses, it provides a simplified approach and is expected to help reduce potential dispensing and dosing errors while meeting the objectives of the weight based dosing. This approach is further supported by the wide margin of safety/efficacy for each DAA.

In the global Phase 3 program, 30 adult HCV GT1-infected subjects had body weight ranging from 42 to 49 kg. The exposures of ombitasvir, paritaprevir, ritonavir and dasabuvir in these subjects were within the ranges of exposures in subjects who had body weight of at least 50 kg. The established safety and efficacy of the 3D regimen in adults would support the use of the same adult dose of ombitasvir/paritaprevir/ritonavir 25/150/100 mg QD and dasabuvir 250 mg BID in children who weigh at least 42 kg. For the present study, children who weigh at least 45 kg will be dosed with adult dose if they are willing to swallow the adult formulations.

For Part 1 of the present study, the proposed doses by body weight range for subjects administered the adult formulation or the mini tablet formulation are shown in [Table 11](#).

**Table 11. Proposed DAA and Ritonavir Doses for Subjects Administered the Adult Formulation or Mini Tablet Formulation**

	Body Weight		
	15 to 29 kg	30 to 44 kg	≥ 45 kg
Paritaprevir (QD)	50 mg	100 mg	150 mg
Ritonavir (QD)	35 mg	70 mg	100 mg
Ombitasvir (QD)	10 mg	15 mg	25 mg
Dasabuvir (BID)	100 mg	150 mg	250 mg

For Part 1, enrollment will start with pediatric subjects  $\geq 12$  to 17 years old who are  $\geq 45$  kg and willing to swallow the adult formulations. The pharmacokinetic and clinical data will be used to confirm appropriate exposure in this age group. Dose adjustments will be made if necessary to ensure safe and efficacious exposures that are comparable to the adult population.

Enrollment in Part 2 will only begin after the recommendations of adult 3D formulation are determined  $\geq 12$  to 17 years based on the pharmacokinetic, safety and efficacy data from Part 1 of the study.

Details on the dose adjustment considerations for Part 1, the enrollment sequence in Part 1, and the considerations for enrollment in Part 2 are provided in Section 5.1.

### **5.6.6 Maximum Dose**

For Part 1, the maximum dose of OBV, PTV and RTV will not exceed 25 mg, 150 mg, and 100 mg per day for 12 weeks. The maximum dose of DSV will not exceed 500 mg per day for 12 weeks. For subject receiving RBV, the maximum RBV dose will not exceed 1200 mg, divided twice daily for 12 weeks.

For Part 2, the maximum dose of OBV, PTV and RTV will not exceed 25 mg, 150 mg, and 100 mg per day for 12 or 24 weeks depending on HCV genotype, sub-genotype and cirrhosis status. For HCV GT1-infected subjects, the maximum dose of DSV will not

exceed 500 mg per day for 12 or 24 weeks. For subject receiving RBV, the maximum RBV dose will not exceed 1200 mg, divided twice daily for 12 or 24 weeks.

## **6.0 Complaints**

A Complaint is any written, electronic, or oral communication that alleges deficiencies related to the physical characteristics, identity, quality, purity, potency, durability, reliability, safety, effectiveness, or performance of a product/device after it is released for distribution.

For adverse events, please refer to Sections 6.1 through 6.1.7.6.

### **6.1 Medical Complaints**

The investigator will monitor each subject for clinical and laboratory evidence of adverse events on a routine basis throughout the study. The investigator will assess and record any adverse event in detail including the date of onset, event diagnosis (if known) or sign/symptom, severity, time course (end date, ongoing, intermittent), relationship of the adverse event to study drug, and any action(s) taken. For serious adverse events considered as having "no reasonable possibility" of being associated with study drug, the investigator will provide an "Other" cause of the event. For adverse events to be considered intermittent, the events must be of similar nature and severity. Adverse events, whether in response to a query, observed by site personnel, or reported spontaneously by the subject will be recorded.

All adverse events will be followed to a satisfactory conclusion.

#### **6.1.1 Definitions**

##### **6.1.1.1 Adverse Event**

An adverse event (AE) is defined as any untoward medical occurrence in a patient or clinical investigation subject administered a pharmaceutical product and which does not necessarily have a causal relationship with this treatment. An adverse event can therefore

be any unfavorable and unintended sign (including an abnormal laboratory finding), symptom, or disease temporally associated with the use of a medicinal (investigational) product, whether or not the event is considered causally related to the use of the product.

Such an event can result from use of the drug as stipulated in the protocol or labeling, as well as from accidental or intentional overdose, drug abuse, or drug withdrawal. Any worsening of a pre-existing condition or illness is considered an adverse event. Worsening in severity of a reported adverse event should be reported as a new adverse event. Laboratory abnormalities and changes in vital signs are considered to be adverse events only if they result in discontinuation from the study, necessitate therapeutic medical intervention, (meets protocol specific criteria [see Section 6.1.7 regarding toxicity management]) and/or if the investigator considers them to be adverse events.

An elective surgery/procedure scheduled to occur during a study will not be considered an adverse event if the surgery/procedure is being performed for a pre-existing condition or the surgery/procedure has been pre-planned prior to study entry. However, if the pre-existing condition deteriorates unexpectedly during the study (e.g., surgery performed earlier than planned), then the deterioration of the condition for which the elective surgery/procedure is being done will be considered an adverse event.

#### **6.1.1.2 Serious Adverse Events**

If an adverse event meets any of the following criteria, it is to be reported to AbbVie as a serious adverse event (SAE) within 24 hours of the site being made aware of the serious adverse event.

Death of Subject	An event that results in the death of a subject.
Life-Threatening	An event that, in the opinion of the investigator, would have resulted in immediate fatality if medical intervention had not been taken. This does not include an event that would have been fatal if it had occurred in a more severe form.

Hospitalization or Prolongation of Hospitalization	An event that results in an admission to the hospital for any length of time or prolongs the subject's hospital stay. This does not include an emergency room visit or admission to an outpatient facility.
Congenital Anomaly	An anomaly detected at or after birth, or any anomaly that results in fetal loss.
Persistent or Significant Disability/Incapacity	An event that results in a condition that substantially interferes with the activities of daily living of a study subject. Disability is not intended to include experiences of relatively minor medical significance such as headache, nausea, vomiting, diarrhea, influenza, and accidental trauma (e.g., sprained ankle).
Important Medical Event Requiring Medical or Surgical Intervention to Prevent Serious Outcome	An important medical event that may not be immediately life-threatening or result in death or hospitalization, but based on medical judgment may jeopardize the subject and may require medical or surgical intervention to prevent any of the outcomes listed above (i.e., death of subject, life-threatening, hospitalization, prolongation of hospitalization, congenital anomaly, or persistent or significant disability/incapacity). Additionally, any elective or spontaneous abortion or stillbirth is considered an important medical event. Examples of such events include allergic bronchospasm requiring intensive treatment in an emergency room or at home, blood dyscrasias or convulsions that do not result in inpatient hospitalization, or the development of drug dependency or drug abuse.

For serious adverse events with the outcome of death, the date and cause of death will be recorded on the appropriate case report form.

### **6.1.2 Adverse Event Severity**

The investigator will rate the severity of each adverse event according to the National Cancer Institute Common Terminology Criteria for Adverse Events (NCI CTCAE Version 4).

The table of clinical toxicity grades "National Cancer Institute Common Terminology Criteria for Adverse Events, Version 4" is available from the Cancer Therapy Evaluation Program (CTEP) website at: [http://evs.nci.nih.gov/ftp1/CTCAE/CTCAE\\_4.03\\_2010-06-14\\_QuickReference\\_5x7.pdf](http://evs.nci.nih.gov/ftp1/CTCAE/CTCAE_4.03_2010-06-14_QuickReference_5x7.pdf) and is to be used in the grading of adverse events. Below are the general grading categories. However, the investigator should always search NCI CTC AE for a given diagnostic/symptomatic AE term to identify and apply specific grading details for that AE entity.

***Grading System for Adverse Events*** (a semi-colon indicates 'or' within the description of the grade).

- Grade 1** Mild; asymptomatic or mild symptoms; clinical or diagnostic observations only; intervention not indicated
- Grade 2** Moderate; minimal, local or noninvasive intervention indicated; limiting age-appropriate instrumental ADL\*
- Grade 3** Severe or medically significant but not immediately life-threatening; hospitalization or prolongation of hospitalization indicated; disabling; limiting self-care ADL\*\*
- Grade 4** Life-threatening consequences; urgent intervention indicated
- Grade 5** Death related to AE

ADL = Activities of Daily Living

\* Instrumental ADL refer to preparing meals, shopping for groceries or clothes, using the telephone, managing money, etc.

\*\* Self-care ADL refer to bathing, dressing and undressing, feeding self, using the toilet, taking medications, and not bedridden.

### **6.1.3 Relationship to Study Drug**

The investigator will use the following definitions to assess the relationship of the adverse event to the use of (OBV/PTV/RTV with or without DSV) and to the use of RBV (if applicable):

- Reasonable Possibility** An adverse event where there is evidence to suggest a causal relationship between the study drug and the adverse event.

**No Reasonable Possibility** An adverse event where there is no evidence to suggest a causal relationship between the study drug and the adverse event.

For causality assessments, events assessed as having a reasonable possibility of being related to the study drug will be considered "associated." Events assessed as having no reasonable possibility of being related to study drug will be considered "not associated." In addition, when the investigator has not reported a causality or deemed it not assessable, AbbVie will consider the event associated.

[figure not shown]
If an investigator's opinion of no reasonable possibility of being related to study drug is given, an "Other" cause of event must be provided by the investigator for the serious adverse event.

#### **6.1.4 Adverse Event Collection Period**

All serious adverse events as well as protocol-related nonserious adverse events (e.g., infection at venipuncture site) will be collected from the time the parent(s)/guardian(s) and subject signs the study-specific informed consent and assent (as appropriate for age and country) respectively until study drug administration. From the time of study drug administration until 30 days following discontinuation of study drug treatment has elapsed, all adverse events and serious adverse events will be collected, whether solicited or spontaneously reported by the subject. From 30 days following discontinuation of study drug administration until the end of study, only serious adverse events deemed related to study drug by the investigator will need to be collected.

Adverse event information will be collected as shown in [Figure 2](#).

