**Part 3 (Long-Term Follow-Up):**

All subjects who have completed Post-Treatment Week 24 in either Part 1 or Part 2 of the study will be followed to assess the durability of viral response, for the emergence and persistence of resistant viral variants, and for SAEs related to study drug for an additional 120 weeks in the Long-term Follow-up period. Study visits will occur at Post-Treatment Weeks 36, 48, 96, and 144.

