- g. Nonserious AEs and all SAEs will be collected until 30 days post dosing. Only drug-related SAEs will be collected thereafter. See Section 6.1.4.
- h. Resistance samples are only collected at the confirmation visit for patients that potentially meet virologic failure criteria.
- i. The Tanner Pubertal stage is assessed for subjects aged  $\geq 9$  to 17 years old. Tanner staging will not be repeated once the child reaches Tanner Stage 5.
- j. Tanner Pubertal Staging only performed at PT Weeks 12, 36, 96 and 144.
- k. The PRO should be administered as the first study procedure at each visit.

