### **Adverse Event of Special Interest**

Specific AEs of special interest will be identified by the following search criteria:

---

Adverse Event of Special Interest	Search Criteria	Time Frame
Hepatic decompensation and hepatic failure	PMQ "Hepatic decompensation and hepatic failure"	Treatment-emergent
Hepatocellular carcinoma	Cases will be identified by the following MedDRA preferred terms: hepatic cancer recurrent, hepatocellular carcinoma, hepatic neoplasm, hepatic cancer, and hepatic cancer metastatic	All post-baseline cases including both treatment emergent and non-treatment emergent
Severe cutaneous reactions	SMQ "Severe cutaneous adverse reactions" (narrow search)	Treatment-emergent

---

For each AE of special interest, the number and percentage of subjects experiencing at least one adverse event of special interest will be presented by SOC and PT. A listing of adverse events for subjects meeting the search criterion will be provided for each adverse event of special interest.

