### **11.2.2 Listing of Adverse Event**

Listings of all serious adverse events (from the time the subject signed the study-specific informed consent until the end of the study), treatment-emergent serious adverse events, treatment-emergent adverse events leading to death, treatment-emergent adverse events leading to discontinuation of study drug, treatment-emergent adverse events leading to study drug interruptions, treatment-emergent adverse events leading to RBV dose modifications and treatment-emergent adverse events of special interest will be provided.

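### The SAP counts hepatocellular carcinoma at any time after baseline, but from 30 days after the last dose the protocol requires only drug-related SAEs, so the count cannot be assured complete

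*Protocol*

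**What the plan says.** **Protocol, collection.** Section 6.1.4 sets two windows once dosing has started. The first is complete: "From the time of study drug administration until 30 days following discontinuation of study drug treatment has elapsed, all adverse events and serious adverse events" are collected. After that and until the end of study, "only serious adverse events deemed related to study drug by the investigator will need to be collected". Footnote g of the post-treatment table in Appendix C repeats the rule ("Only drug-related SAEs will be collected thereafter"). The synopsis describes Part 3 in the same terms, as follow-up "for SAEs related to study drug for an additional 120 weeks in the Long-term Follow-up period".

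**SAP, reporting.** The section on adverse events of special interest (11.2.1.1) has three rows. Hepatic decompensation/failure and severe cutaneous reactions are limited to treatment-emergent events. HCC alone has the time frame "All post-baseline cases including both treatment emergent and non-treatment emergent". On the source, the SAP says "Cases will be identified by the following MedDRA preferred terms" and names five terms. The output is the number and percentage of subjects, plus a listing. Separately, SAP 11.2.2 promises "Listings of all serious adverse events (from the time the subject signed the study-specific informed consent until the end of the study", which is a listing and not a count.

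**Imaging.** Protocol 5.3.1.1 and Appendix C schedule liver ultrasound for subjects with compensated cirrhosis only, yearly after Day 1. SAP 4.2 names ultrasound as the HCC assessment, but no SAP section analyses its results.

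**The concern.** SAP 11.2.1 ends the treatment-emergent period 30 days after the last dose. By taking HCC beyond treatment-emergent events, the SAP reaches into the period in which the protocol stops requiring unrelated events. In that period the extension is sure to pick up only cases that an investigator attributes to study drug.

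What is at stake is the meaning of the result. The table would be headed as all post-baseline HCC, and its most likely entry is zero. A zero drawn from drug-related reports alone does not show that no HCC occurred; it may only show that none was attributed to study drug. Protocol 3.1 and 5.1.4 give long-term safety as a purpose of Part 3, so a reader may lean on that zero.

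**Working it through.** **1. Reproduce the stated duration (SAP 4.2).** Treatment weeks plus 144 post-treatment weeks: 12 + 144 = 156 and 24 + 144 = 168. Both match the SAP.

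**2. Length of the restricted window.**
- Post-treatment days: 144 × 7 = 1,008.
- Less the 30 days of full collection: 1,008 − 30 = 978.
- Share of post-treatment time: 978 / 1,008 = 97.0%.
- Share of time from first dose: 978 / (156 × 7) = 978 / 1,092 = 89.6% for 12-week regimens, and 978 / (168 × 7) = 978 / 1,176 = 83.2% for 24-week regimens.

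**3. Sensitivity to the length of Part 3.** Protocol 5.1 and 5.1.4 can be read as a Part 3 that itself lasts 144 weeks after Post-Treatment Week 24. That gives (24 + 144) × 7 = 1,176 post-treatment days, of which 1,176 − 30 = 1,146 are restricted. The 978-day figure is the smaller of the two.

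**4. How many cases could be involved.** The documents give no HCC rate, so the rates below are assumptions. With about 62 subjects and full follow-up, the restricted window holds 62 × 978 / 365.25 = 166.0 person-years. Expected cases = rate × 166.0, and the chance of at least one = 1 − exp(−expected).

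| Assumed HCC rate per 100 person-years | Expected cases in the window | Chance of at least one |
|---|---|---|
| 0.1 | 0.17 | 15% |
| 0.5 | 0.83 | 56% |

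These are upper limits on what could be lost, because a case judged related, or recorded anyway, is kept. The protocol's introduction says that HCC has rarely been reported in adolescents, which points to the first row or below.

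**5. Whether another source closes the gap.**
- Part 1 enrols only non-cirrhotic subjects, so about 36 of about 62 (58%) have no HCC imaging by design, as do any non-cirrhotic subjects in Part 2.
- For cirrhotic subjects, the documents do not say that an HCC confirmed on imaging must be entered as an adverse event if judged unrelated, and the SAP search uses coded terms.
- After 30 days, concomitant medication is recorded only for related SAEs and HCV treatment (Protocol 5.2.3), so it gives no indirect signal of an unrelated HCC.

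**The case against.** The strongest reply is that the protocol does not bar unrelated late events. Section 6.1.5 tells the investigator to report an SAE through the EDC system within 24 hours whether or not it is associated with study drug, and it gives no end date. Section 6.1 has investigators monitor for adverse events throughout the study. Section 6.1.4 states what needs to be collected, which is a minimum. Section 6.1.3 treats missing or non-assessable causality as associated, so only events actively judged unrelated are at risk. All of this stands, and it rules out two inferences that a reader might draw: that an unrelated late HCC can never reach the data, and that the count will be incomplete. The documents support only that such a case need not be recorded. Section 6.1.5 does not settle the matter, because it sets the reporting route and clock, while 6.1.4 and footnote g set the window.

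A reader might also infer that the SAE listing in SAP 11.2.2 contradicts the protocol in the same way. It need not. It is a listing, and Protocol 8.1.6 speaks of listing SAEs recorded in Part 3. Read with that, it can be complete for what it claims.

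It can also be said that the HCC time frame is only an analysis filter, and that limiting late collection to related SAEs is deliberate and consistently stated. The collection rule is indeed a legitimate choice. But a number and percentage described as all post-baseline cases will be read as ascertainment unless the table states the rule.

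**Conclusion.** The point holds as a mismatch between one SAP output and the protocol's collection rule. Followed as written, the plan yields an HCC count that depends on the investigator's causality opinion over 978 of 1,008 post-treatment days, so its completeness cannot be assured. The 978 days rest on SAP 4.2's 144 post-treatment weeks and on full follow-up.

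The 97% is a share of calendar time and should not be read as a share of events missed. Few if any HCC cases are expected, and the documents give no rate from which to put a firm number on the loss. The consequence is confined to what the long-term HCC result, and above all a zero, can be taken to mean. SVR12 and the pharmacokinetic endpoints do not use these data. The correction is worth making because it is cheap for its effect on that interpretation.

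**What to change.** **Preferred.** In Protocol 6.1.4 and Appendix C footnote g, require the five HCC preferred terms named in the SAP to be recorded through Post-Treatment Week 144 regardless of causality. In the same change, reconcile 6.1.5 with 6.1.4 and footnote g by stating whether unrelated SAEs after 30 days are to be reported. The cost is a protocol amendment, with ethics committee approval under Protocol 9.1 at up to 30 sites, and an eCRF completion note. No visits are added, since Appendix C already schedules an adverse event assessment at the post-treatment visits through Week 144.

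**If that is not done.** Footnote the HCC table: *after 30 days post-dose, only SAEs judged drug-related were required to be collected*. Put the same footnote on the SAE listing in SAP 11.2.2. This is a SAP edit only, but it leaves the count itself unassured. Because the preferred change reaches only the HCC terms, the listing footnote would remain apt for other SAEs in either case, unless the reconciliation with 6.1.5 widens their collection.
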